Study Objectives:	
The primary objective of this research is to assess the human factors in relabeling the SaliPen from a prescription-based device to an OTC.
 
Primary performance endpoints:
 
• The user can select the device properly.• The user can use the device as instructed in the IFU.
Study Design:	
This will be a single-center, prospective, open-label study.
 
Screening: Eligible subjects will be included in the study.

Test Participant Recruitment Plan:	
Patients visiting the participating clinic will be asked to participate in the study sequentially (by order of recall or arrival at the clinic).
 
For Phase I, enrollment will be stopped once the goal of eight (8) subjects with xerostomia and eight (8) subjects without xerostomia has been reached.
 
For Phase II, 16 subjects with xerostomia that are evaluated or treated at the clinic will be enrolled sequentially (by order of recall or arrival at the clinic). Patients that have participated in Phase I and have xerostomia will be invited to participate in Phase II, as well.
 
Participants will receive \$25 cash for participating in either phase of this study. Participants in both phases will receive \$50 cash.

	Participants in Phase II will be given the option to keep the SaliPen device they will use in the study.
Inclusion Criteria:	Phase I: Any adult person that is 18 years old or older Phase II: Subjects with xerostomia that are 18 years old or older
Exclusion Criteria:	Phase I: 
• Children and adolescents (persons under 18 years of age)• Persons with experience in the use of SaliPen Phase II: 
• Persons with experience in the use of SaliPen• Children and adolescents (persons under 18 years of age)• Epileptic disorder• Persons that are allergic to the surface materials of the device
◦ Electrodes: coated with gold◦ Body: made of methyl vinyl silicone rubber• Use of a pacemaker• Pregnancy• Psychiatric or psychological disorders• Involuntary muscle movement disorder (such as Parkinson's)• Neurologic disorder in head and neck area
Medical Device Description:	Electrical salivary stimulator system.
Study Endpoints:	Performance Endpoints: 
• Correct selection of the product.• Product use in accordance with the IFU.

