3.2. The study rationale

- Xerostomia (dry mouth) is the subjective feeling of oral dryness. The diagnosis by the practitioner is mostly relying on the patient's feeling.
- Most patients are elderly, many of them with limited mobility.
- Nowadays, those patients are at high risk for COVID-19 infection, morbidity and even mortality.
- The fear of exposure at the practitioner's clinic to obtain an Rx inhibits them from treating their xerostomia with the SaliPen.
- The cost of getting a prescription is an additional burden.
- The SaliPen is an OTC in other parts of the world for years.
- The performance of potential American users of an OTC SaliPen device will be evaluated in this usability study.

As a result, many patients leave their oral dryness untreated, with the well-known consequences of poor oral functions, oral health, daily suffering, and more.

4. Brief Study Description

This Human Factors Validation Testing will assess user interactions to verify the capability of potential users to assess if the study product fits their needs and if they can use it correctly based on the provided Information For User (IFU)?

More specifically, this is a non-comparative case series study and is subdivided into two major parts. Those parts are:

- 1- Phase I: aimed at testing if, based on the IFU, the potential subjects can decide whether the study product is or is not appropriate to treat their condition and,
- 2- Phase II: aimed at assessing whether the users can use the study product correctly without counseling by a health care provider.

Condition or disease	Intervention/treatment
Xerostomia	SaliPen

5. Detailed Study Description

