5.1. Phase I

To simulate an OTC setting, potential subjects will be requested to read the label text on the outside of the study product package (external labeling) and determine whether the study product addresses their needs, without a provider direction or assistance.

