5.2. Phase II

The study product will be dispensed only to those subjects who will indicate that they volunteerize to participate in this phase of the study.

At Phase II subjects with xerostomia and that are willing to try the study product, will be requested to use it with no training, except for their understanding of the User Manual (internal labeling). Those subjects will use the study product in a supervised clinical setting. Subjects who report any discomfort will be offered the option to pause and remove the device upon such a request.

Correct use verification will be performed by the study investigators. Subjects will answer questions regarding product use, clarity of the IFU, ease of use, etc. Subjects will also receive an exam of their oral cavity.

6. Study Design

Study Type:	Interventional (Clinical Trial)
Enrollment:	Phase I: 16 participants, 8 with xerostomia and 8 without xerostomia
	Phase II: 16 participants with xerostomia (may include participants in Phase I with xerostomia)
Allocation:	N/A
Intervention Model:	Single Group Assignment
Masking:	None (Open Label)
Primary Purpose:	Human Factor Validation - Usability Engineering assessment for OTC labeling
Official Title:	SaliPen Usability Engineering Study for OTC labeling
Study Start Date:	TBD

According to the FDA Guidance document “Applying Human Factors and Usability Engineering to Medical Devices”, a sample of 15 people to detect most of the problems in a user interface constitutes a practical minimum number of participants for human factors validation testing. This sample size theoretically provides the best possibility of detecting user interface design flaws while limiting the amount of resources required.

7. Arms and Interventions

Arm	Intervention/treatment
Experimental: Use of SaliPen medical device	Use according to self-decision.

8. Features to be studied

The points of interaction between the user and the device (User Interface) will be evaluated, including:

- the elements of the device with which the user interacts (i.e., those parts of the device that users see and touch), and
- the IFU (including packaging, labeling, User Manual, etc.).

The following parameters will be studied:

- Hazard: Potential source of harm, if any.
- Use error: User action or lack of action that was different from that expected by the manufacturer.

9. Outcome Measures

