1. Percentage of participants who appropriately will self-select the study product for use under simulated OTC conditions [Phase I]. Following the standard norms for the Rx-to-OTC switch process, this outcome is a validation of potential consumers' ability to self-diagnose the condition and to decide that treatment with the product is appropriate for them.
2. Percentage of participants who correctly will use the study product when dispensed under simulated OTC conditions [Phase II]. Correct use means that the participants will demonstrate the use of the study product according to the guidelines outlined in the User Manual. Following the standard norms for the therapy of Rx-to-OTC switch process, this outcome is a validation of potential consumers' ability to self-treat with the product according to the product's supplied IFU.

10. Eligibility Criteria

Ages Eligible for Study: 18 years of age and older for Phase I and Phase II

Genders Eligible for Study: Female and male

10.1. Inclusion criteria:

- 1- For Phase I: 8 subjects with xerostomia and 8 without that are 18 years old or older
- 2- For Phase II: Subjects with xerostomia that are 18 years old or older

10.2. Exclusion criteria:

- 1- For Phase I:
 - Children and adolescents (persons under 18 years of age)
 - Persons with experience in the use of SaliPen

2- For Phase II: Subjects for whom the study product is not indicated and/or do not agree to participate in Phase II. For the avoidance of doubt, the following conditions are exclusion criteria:

- Persons with experience in the use of SaliPen
- Children and adolescents (persons under 18 years of age)
- Epileptic disorder
- Persons that are allergic to the surface materials of the device
 - Electrodes: coated with gold
 - Body: made of methyl vinyl silicone rubber
- Use of a pacemaker
- Pregnancy
- Psychiatric or psychological disorders
- Involuntary muscle movement disorder (such as Parkinson's)
- Neurologic disorder in head and neck area

11. Reportable Events

An adverse event (AE) is defined as any untoward medical occurrence in a subject during the investigation. Any findings will be documented on the AE CRF.

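### Both phases exclude prior users of SaliPen but not clinic patients who were prescribed, shown or counselled on it without using it, and the plan does not record such exposure

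*Combined protocol and SAP*

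**What the plan says.** The synopsis (section 2) and section 10.2 list, for both phases, the exclusion "Persons with experience in the use of SaliPen". Experience in use is not defined. The remaining exclusions concern age and, for Phase II, medical conditions, allergy, indication and willingness; the general Phase II clause reads "Subjects for whom the study product is not indicated and/or do not agree to participate in Phase II". None mentions an earlier prescription, demonstration or conversation about the device.

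The study question is framed as the absence of professional help. Section 5.1 has Phase I participants "determine whether the study product addresses their needs, without a provider direction or assistance". Section 4 describes Phase II as "aimed at assessing whether the users can use the study product correctly without counseling by a health care provider". Section 5.2 says that Phase II participants "will be requested to use it with no training, except for their understanding of the User Manual".

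On recruitment, the synopsis gives the objective as "to assess the human factors in relabeling the SaliPen from a prescription-based device to an OTC", so the device is at present obtained through a provider. Participants in both phases are patients of the participating clinic, approached in sequence. For Phase II, "16 subjects with xerostomia that are evaluated or treated at the clinic will be enrolled sequentially". Phase I participants with xerostomia are invited to continue into Phase II.

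The Phase I anamnesis in section 16 records xerostomia, contraindications and precautions. The Phase II sheet records two oral examinations and seven scored items. Neither asks about prior contact with the device. The analysis consists of descriptive percentages.

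**The concern.** By excluding prior users, the plan accepts that familiarity with the device would contaminate the result. The criterion stops short of that logic, because familiarity can also come from a prescriber's explanation or a demonstration. The no-assistance and no-training conditions in sections 5.1 and 5.2 govern the study session; they do not screen out instruction received earlier.

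A retail buyer would not have had that instruction. A participant who was told the device's purpose and warnings is better placed in Phase I, and one who was told how it is operated is better placed on Phase II items 1 to 5. With 16 people per phase and a fixed success threshold, a few such participants could change the conclusion. Because exposure is not recorded, a reader of the results could not tell whether this had happened.

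**Working it through.** **The plan's own figures.** There is no power calculation to reproduce: 16 per phase meets the practical minimum of 15 cited in section 6. The thresholds in section 13 are consistent with the evaluation sheet:

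- Phase II pass for one participant: 0.85 × 7 = 5.95, so 6 of 7, as section 16 states.
- Study success per phase: 0.85 × 16 = 13.6, so 14 of 16 (13/16 = 81.3% fails; 14/16 = 87.5% passes).

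**Does any other text close the gap?** The synopsis, sections 5.1, 5.2, 10.1 and 10.2, and the questionnaires and sheets in sections 15 and 16 contain no criterion or question on prior prescription, demonstration or counselling. A broad reading of experience in use might take in a hands-on trial. It would not take in a prescription or a verbal explanation.

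**How sensitive is the threshold?** Three inputs are assumptions that the documents do not give: the number exposed among the 16 (*k*), the pass probability of an uninstructed participant (*t*), and that of an exposed participant (*e*). With participants independent,

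P(success) = Σ over j = 0..k of C(k, j) e^j (1−e)^(k−j) × P[Bin(16−k, t) ≥ 14−j].

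For *t* = 0.75:

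- *k* = 0: P[Bin(16, 0.75) ≥ 14] = 0.1336 + 0.0535 + 0.0100 = 0.197.
- *k* = 2, *e* = 1: P[Bin(14, 0.75) ≥ 12] = 0.281.
- *k* = 2, *e* = 0.90: 0.81 × 0.2811 + 0.18 × 0.1010 + 0.01 × 0.0178 = 0.246.
- *k* = 4, *e* = 1: P[Bin(12, 0.75) ≥ 10] = 0.2323 + 0.1267 + 0.0317 = 0.391.
- *k* = 4, *e* = 0.95: 0.346.

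The same formula over a wider range:

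| Uninstructed pass rate *t* | None exposed | 2 exposed, *e* = 0.90 | 2 exposed, *e* = 1 | 4 exposed, *e* = 0.95 | 4 exposed, *e* = 1 |
|---|---|---|---|---|---|
| 0.70 | 0.099 | 0.139 | 0.161 | 0.221 | 0.253 |
| 0.75 | 0.197 | 0.246 | 0.281 | 0.346 | 0.391 |
| 0.80 | 0.352 | 0.399 | 0.448 | 0.503 | 0.558 |

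At *t* = 0.75 with four participants who always pass, the expected observed pass rate is (12 × 0.75 + 4)/16 = 81.3% instead of 75%.

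**The case against.** The strongest reply is that the affected group may be very small or empty. No text says that this clinic prescribes, demonstrates or counsels on SaliPen, and section 12 describes general oral health settings. Section 3.2 suggests limited uptake, since cost and fear of a visit keep patients from obtaining a prescription. Anyone who was prescribed the device and used it is already excluded, and half of the Phase I sample has no xerostomia. This stands: the size of the problem is unknown.

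The second reply is that the tests leave limited room for remembered instruction. In section 15, Phase II participants read the manual first, items 1 to 5 cite manual pages, and item 3 also points to a video. The Phase I questionnaire itself names the indication and lists the warnings. Two of the seven Phase II points are self-reports of discomfort and difficulty, which earlier counselling cannot secure. This stands too. It makes *e* = 1 a worst case, and it may mean that uninstructed users already do well. At *t* = 0.90, two certain passers move the chance of success only from 0.789 to 0.842.

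Two stronger readings are tempting, and the documents support neither:

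- A reader might infer that Phase II draws on people already treated for dry mouth and probably introduced to SaliPen there. The synopsis says only that participants have xerostomia and are evaluated or treated at the clinic. It does not say for what, or that the device was discussed.
- A reader might infer that the bias can only favour passing. A xerostomia patient who was offered the device and declined it might answer that it does not fit their needs. That could fail Phase I, where every answer must be correct.

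Neither reply closes the gap in the criterion, and both leave the exposure unrecorded.

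**Conclusion.** The gap is real and applies to both phases. The prior-exposure criterion covers use only, while the study asks about selection and use without professional direction. In Phase I the concern falls mainly on the eight participants with xerostomia.

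Exposure would tend to raise pass rates, by an amount that the documents do not fix. If nobody is exposed, the effect is nil. On the assumptions tabulated, two exposed participants add roughly 4 to 10 percentage points to the chance of meeting the 14-of-16 rule, and four add roughly 12 to 21. These figures show that the threshold is sensitive; they do not estimate what will happen at this clinic. They rest on assumed counts and pass rates and on independence between participants. The point is worth settling before enrolment because the remedy is cheap and the exposure is not otherwise collected.

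**What to change.** In the synopsis and section 10.2, for both phases, replace the criterion with: *Persons who, before enrolment in this study, have used, been prescribed, been shown or been counselled on SaliPen.* The words on enrolment are needed because Phase I participants study the package and are invited into Phase II; without them the criterion would bar those participants. Ask it as one screening question that does not name the indication, so that Phase I item 1 is not given away. The criterion should not extend to other intraoral stimulators: nothing in the documents supports that, and the phrase hints at the indication.

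If the sponsor prefers not to exclude these patients, the minimum is to add a prior-exposure field to the evaluation sheets and report pass rates in each phase with and without exposed participants.

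The cost is one reworded criterion and one screening question. The sample size does not change. A few clinic patients may become ineligible, so recruitment may be slightly slower.

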Statistical Analysis	A simple descriptive statistical analysis will be utilized to calculate the percentage of correct answers and the percentage of subjects that passed the evaluation in each phase of the study.

3. Study Objective and Rationale

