Serious AEs include any events resulting in death, decreased life expectancy, life-threatening situations, persistent or permanent disability/incapacity, hospitalization, or congenital anomaly/birth defect or other important medical event. Within 24 hours, the Investigator will submit a written report documenting the circumstances of the serious AE.

While AE's and SAE's are not anticipated, should an incident occur during the visit or a subject report an event following the visit, the AE will be recorded in the subject's study records and followed to resolution.

12. Contacts and Locations

The subjects will randomly be recruited at clinical settings that deal with oral health, like dental or head and neck clinics. The outcome measure will be performed in this setting. Data will be collected on-site by the clinical staff.

13. Task Analysis

The Task Analysis breaks down the device use process into discrete sequences of tasks. The tasks will be analyzed to identify the user interface components involved, the use errors that users could make and the potential results of all use errors. The following task analysis is planned:

Phase	#	Task
I	1	Potential user knows the intended use of the study product.
	2	Potential user assesses correctly whether the study product is indicated for him/her.
	3	Potential user assesses correctly whether he/she can use the study product or not or conditioned to a medical advice.
II	1	User knows the maximum amount of times and the maximum length of time he/she can use the study product.
	2	User knows how to switch the study product ON and OFF.
	3	User knows how to place the study product into his/her mouth.
	4	User knows how to remove the study product from his/her mouth.
	5	Patient knows how to separate the intraoral and the extraoral units.
	6	Patients reports any significant discomfort felt with SaliPen
	7	Patients reports any significant difficultis in using SaliPen

Each task will be evaluated by the binary grading scheme satisfactory/unsatisfactory. The evaluator will be a member of the study team.

For Phase I - 100% success is needed to pass the evaluation for every subject.

For Phase II - 85% success rate is needed to pass the evaluation for every subject.

The Human Factor Study will be considered successful if 85% of the participants passed each Phase of the test.

14. Ethical and Legal Aspects

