Gingival Mucosa			_____
Edentulous Ridge/Retromolar area			_____
Tongue			_____
Sublingual Area/floor of mouth			_____
Submandibular area			_____

Step 2: Assessment of subject performance
EVALUATOR NAME: _____

DATE: _____

Please evaluate how the participant addresses the following questions/tasks:

Questions	Participant's answer	Correct answer	Success (1) / Failure (0)
1. How many times in a day and how many minutes (maximum time) you can use the device in one session?			
Tasks	Evaluation		Success (1) / Failure (0)
2. How do you turn on ON and OFF the device?			
3. How do you insert the device in your mouth?			
4. How do you take the device out of your mouth?			
5. How do you detach and reattach the white extraoral command unit from the blue intraoral stimulating unit?			
Subject assessment (place an x where relevant for you) Note: Success (1) is meant if options 2 or 3 were chosen Failure (0) is meant if option 1 was chosen			Success (1) / Failure (0)
6. Did you experience discomfort with the SaliPen in your mouth?	1- Severe discomfort 2- Moderate discomfort 3- No discomfort		
7. Did you experience difficulties in using the SaliPen?	1- Severe discomfort 2- Moderate discomfort 3- No discomfort		

Summary evaluation:
Total questions/tasks/self-assessments: 7

Number of points: _____

Passed? (minimum 6 points):

Yes
 No

Step 3: Oral soft tissue examination

EVALUATOR NAME: _____

DATE: _____

	Normal	Abnormal	If Abnormal, please specify findings
Labial Mucosa (including lips)			
Buccal Mucosa			
Mucogingival Folds			
Gingival Mucosa			
Edentulous Ridge/Retromolar area			
Tongue			
Sublingual Area/floor of mouth			
Submandibular area		

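### Phase II items 6 and 7: section 13 states no cut for discomfort or difficulty, and the planned percentages cannot separate moderate from none

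*Combined protocol and SAP*

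**What the plan says.** Section 13 (Task Analysis) lists Phase II task 6 as "Patients reports any significant discomfort felt with SaliPen" and task 7 as "Patients reports any significant difficultis in using SaliPen". On grading it says: "Each task will be evaluated by the binary grading scheme satisfactory/unsatisfactory". It does not define the word significant, and it does not say which report counts as satisfactory.

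The Phase II evaluation sheet (section 16, Step 2) turns these tasks into self-assessments with three options: "1- Severe discomfort 2- Moderate discomfort 3- No discomfort". Its scoring note reads "Success (1) is meant if options 2 or 3 were chosen" and "Failure (0) is meant if option 1 was chosen". The same discomfort options are printed under item 7, although that question asks about difficulties in using the device.

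A subject passes Phase II with at least 6 of 7 points on the sheet (85% in section 13). The study succeeds if 85% of participants pass each phase. The Synopsis limits the analysis to descriptive statistics that "calculate the percentage of correct answers and the percentage of subjects that passed the evaluation in each phase of the study".

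**The concern.** There are three linked problems.

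- **Direction.** Section 13 describes an act of reporting. Read literally, a subject who reports severe discomfort has completed the task, yet the sheet gives that subject 0.
- **Threshold and visibility.** Section 13 gives no cut, and the sheet fails only the worst of three grades. Moderate earns the same point as none, and both planned percentages are built from those points. Section 8 lists hazards among the parameters to be studied, and section 5.2 says subjects will be asked about ease of use. The planned summaries show neither in graded form.
- **Scale.** Item 7 cannot record graded difficulty, because its answers are grades of discomfort.

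At stake is whether a reader of the Phase II result, in a study meant to support a switch to over-the-counter labelling, can tell a device that users found comfortable and easy from one that most found moderately uncomfortable.

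**Working it through.** **Inputs.** Seven scored items and a pass mark of 6 points (section 16); 85% per subject and 85% of participants (section 13); 16 Phase II participants (section 6); severe = 0, moderate = 1, none = 1 (section 16 scoring note).

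**Reproducing the plan's pass mark.** 0.85 × 7 = 5.95, so 6 points are needed. 6/7 = 85.7% passes and 5/7 = 71.4% fails. The sheet and section 13 agree here.

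**Participants needed for study success.** 0.85 × 16 = 13.6, so 14. 14/16 = 87.5% meets the criterion and 13/16 = 81.3% does not.

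**Scores for a subject with items 1 to 5 correct.** The last column is hypothetical: the documents state no such rule.

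| Items 6 and 7 | Sheet's rule | If moderate scored 0 |
|---|---|---|
| none, none | 7, pass | 7, pass |
| moderate, none | 7, pass | 6, pass |
| moderate, moderate | 7, pass | 5, fail |
| severe, none | 6, pass | 6, pass |
| severe, moderate | 6, pass | 5, fail |
| severe, severe | 5, fail | 5, fail |

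**What the planned percentages show.** Suppose all 16 subjects have items 1 to 5 correct and choose moderate on both items. Correct answers are 16 × 7 = 112 of 112 (100%), and passes are 16 of 16 (100%). If all 16 choose none on both, the figures are identical.

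Even a severe rating on one item does not fail an otherwise perfect subject (6/7). It does lower the percentage of correct answers.

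**Sensitivity to the undefined cut.** Under the hypothetical rule, three subjects with moderate on both items in an otherwise perfect Phase II give 16 − 3 = 13 passes. 13/16 = 81.3% is below 85%. Moderate on one item only changes no pass result for a subject who is otherwise perfect.

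**The case against.** The strongest reply is that there is only one cut. Section 13 names the tasks in shorthand, and the sheet supplies the rule. A sheet that reads significant as severe is compatible with section 13. With no grade between none and moderate, a subject with mild discomfort may well tick moderate, so failing every moderate answer could penalise complaints that few would call significant. Section 9 also defines the Phase II outcome as using the device as the User Manual describes, and discomfort is not incorrect use.

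Most of this stands, and it rules out three stronger readings that a reader might infer:

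- **That section 13 sets a stricter mark which the sheet contradicts.** It leaves the term undefined, so it sets no rival cut.
- **That the study's success would flip.** The 13/16 result needs a rule that moderate fails, three subjects with moderate on both items, and everything else perfect. The documents state no such rule and give no expected frequency of such ratings.
- **That moderate ratings are lost.** The sheet records the option chosen, section 11 provides for adverse events to be documented on a case report form, and the mouth is examined before and after use. What is lost is visibility in the planned percentages.

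The reply does not meet the narrower point. None of these other routes promises a tabulation of the three grades, the literal wording of section 13 still runs opposite to the scoring, and item 7 still carries the wrong answer scale. The argument from section 9 favours showing the ratings beside the pass rate. It does not favour a second pass rate with moderate scored 0, which this review does not ask for.

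**Conclusion.** The concern holds as an undefined threshold and a gap in reporting. It is not a proven contradiction between two cuts. Under the sheet's rule, Phase II can report 100% correct and 100% passed whether all 16 subjects answer none or all answer moderate on items 6 and 7. This assumes only that items 1 to 5 are correct, and that the analysis is the two percentages named in the Synopsis. Section 13 and the sheet need one common wording, and item 7 does not measure what it asks. Nothing here shows which cut is right or that the study would fail. The point is a low-cost improvement to make before enrolment.

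**What to change.** Before the first subject is enrolled:

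1. Reword tasks 6 and 7 in section 13 as ratings by the subject. State one cut, in the same words, in section 13 and on the sheet. The choice of cut is the sponsor's.
2. Give item 7 answer options worded as degrees of difficulty.
3. Add to the planned analysis a table of items 6 and 7 in all three grades (n/16 each), shown beside the Phase II pass rate.

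The cost is a few words in section 13, one corrected line on the form, and one small table from answers the sheet already collects. IRB approval of the amendment is needed (section 14.4). The downside is that the usability result may look less favourable. If the form is changed after enrolment starts, item 7 would mix two answer scales.

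### Outcome 2 (correct use) has no stated derivation, and the only Phase II subject-level score, a 6-of-7 composite that includes two self-ratings, does not measure it

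*Combined protocol and SAP*

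**What the plan says.** - **Endpoint.** Section 2 (Study Synopsis) lists as a primary performance endpoint: "The user can use the device as instructed in the IFU". Section 9, item 2, makes this a percentage of participants and adds: "Correct use means that the participants will demonstrate the use of the study product according to the guidelines outlined in the User Manual". It does not list the items that count.
- **Conduct.** Section 5.2 states: "Correct use verification will be performed by the study investigators". It continues: "Subjects will answer questions regarding product use, clarity of the IFU, ease of use, etc".
- **Subject-level rule.** Section 13 grades each of seven Phase II tasks as satisfactory or unsatisfactory and sets the pass mark: "For Phase II - 85% success rate is needed to pass the evaluation for every subject". The Phase II sheet in section 16 totals seven points and passes a subject with at least 6.
- **Items.** Item 1 is a knowledge question on maximum use. Items 2 to 5 are tasks: switching on and off, insertion, removal, and detaching and reattaching the units. Items 6 and 7 are the subject's own ratings; the worst of three options scores 0 and the other two score 1.
- **Task 7.** Section 13 describes it as: "Patients reports any significant difficultis in using SaliPen". The matching item in section 16 asks about difficulties, but its three scored options are levels of discomfort.
- **Study-level rule.** "The Human Factor Study will be considered successful if 85% of the participants passed each Phase of the test" (section 13).
- **Use errors.** Section 13 also says: "The tasks will be analyzed to identify the user interface components involved, the use errors that users could make". It does not link that analysis to the success rule.
- **Planned statistics.** Section 2 plans, for each phase, the percentage of correct answers and the percentage of subjects who passed. It does not say whether correct answers are pooled over items or shown item by item.

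**The concern.** The stated endpoint is demonstrated use. The score available to represent it also counts how the subject felt, gives every item the same weight, and tolerates one miss on any item. No item has its own criterion.

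Because the plan does not say how Outcome 2 is obtained from the item scores, a statement that at least 85% of subjects passed Phase II could be read as at least 85% correct use, which it does not establish. A failure concentrated on one task is also what a human factors validation should bring out. Section 6 justifies the sample size by the detection of user interface design flaws. Such a failure would be in the item data, but it might not appear in the planned summaries.

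**Working it through.** **Inputs.** 7 items, pass at 6 points (section 16); 85% per subject and 85% of participants (section 13); 16 Phase II subjects (section 6).

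**1. The plan's own thresholds.**
- Subject: 0.85 × 7 = 5.95, so 6 of 7 (6/7 = 85.7%; 5/7 = 71.4%). This matches the sheet.
- Study: 0.85 × 16 = 13.6, so 14 of 16 (14/16 = 87.5%; 13/16 = 81.3%).

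**2. Which patterns pass.** Seven binary items give 2^7 = 128 patterns. A total of at least 6 means no miss (1 pattern) or exactly one miss (7 patterns), so 8 patterns pass.
- The single miss falls on items 1 to 5 in 5 of the 8.
- If only items 2 to 5 count as use, it falls on them in 4 of the 8.
- A subject with both self-ratings scored 1 passes with 4 of the 5 use items (80%).
- In the other direction, exactly one pattern has items 1 to 5 all correct and fails: items 6 and 7 both 0, total 5/7.

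**3. One task failed by everyone.** Suppose all 16 subjects fail the same use item and score the other six.
- Each has 6/7, so 16/16 pass. On that task 0/16 are correct, and 0/16 have all five use items correct.
- Correct answers pooled over items: (16 × 7 − 16)/(16 × 7) = 96/112 = 85.7%.
- One miss per subject scattered over different items also gives 16/16 and 96/112. The pooled figures cannot tell the two cases apart; a by-item tabulation would.

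**4. Task failures still count through the totals.** If all 16 fail task 3 and 3 of them also fail task 4, those 3 score 5/7. Then 13/16 pass and Phase II fails.

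**5. Sensitivity, on assumed rates only.** One task is failed by everyone and each of the other six items has success rate p. With independent items, P(subject passes) = p^6. If misses on the other six always fall in the same subjects, P(subject passes) = p.

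| p | p^6 | P(at least 14/16 pass), independent | P(at least 14/16 pass), fully clustered |
|---|---|---|---|
| 0.99 | 0.941 | 0.94 | >0.99 |
| 0.98 | 0.886 | 0.73 | >0.99 |
| 0.95 | 0.735 | 0.16 | 0.96 |
| 0.90 | 0.531 | 0.004 | 0.79 |

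**6. No single bad task, on assumed rates only.** Use items are independent with success rate p, and items 6 and 7 always score 1. Then P(pass) = p^5 + 5p^4(1 − p), and P(all five correct) = p^5.

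| p | Pass | All five correct |
|---|---|---|
| 0.98 | 99.6% | 90.4% |
| 0.95 | 97.7% | 77.4% |
| 0.90 | 91.9% | 59.0% |

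**The case against.** **No passage equates the composite with Outcome 2.** This stands. A reader might infer that the sponsor has defined correct use as 6 of 7 points. The documents do not say so, and section 9 plans Outcome 2 as a participant percentage in its own right. The defect is that this percentage has no stated derivation and the one available score does not fit it.

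**Section 5.2 draws no clean line between investigator-verified use and subject-reported ease.** This also stands: product use is among the topics that subjects answer questions about. The mismatch rests on the definition in section 9 and the scoring in section 16, not on section 5.2.

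**By-task information is partly planned.** Tasks are graded singly, section 8 lists use error as a parameter, and section 13 promises a use-error analysis. A reader might infer that the planned statistics would necessarily hide a failed task. That holds only if correct answers are pooled over items, and the plan does not specify pooling.

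**The 16/16 case is an extreme.** It needs every subject to be perfect on the other six items. Under independence, the chance of still reaching 14/16 falls to 0.16 at 95% per item and 0.004 at 90%. It is a counterexample, not a forecast. Nor do the documents support calling two worst self-ratings in one subject either rare or common.

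**One-miss tolerance is a legitimate, prespecified choice.** This stands. A reader might infer that the pass mark should be 5 of 5, or that each task needs its own pass criterion. The documents require neither; both are matters of sponsor preference.

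**All five correct is not the documents' definition.** Section 9 lists no items and item 1 tests knowledge, so the sponsor must confirm the mapping. The conclusion survives either mapping (5 of 8 or 4 of 8).

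**Conclusion.** The point holds as a gap in endpoint derivation and reporting, and should be fixed. Outcome 2 has no rule linking it to the item scores, and the 6-of-7 composite cannot stand in for it: a pass is compatible with a failed use item, and a 100% pass rate is compatible with nobody performing one task correctly. The pattern counts and the 16/16 against 0/16 result follow from the scoring rules alone. The probabilities rest on assumed item rates and on assumptions about dependence, so they do not estimate how large the gap will be in this study.

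The arithmetic of the 6-of-7 threshold is correct. Separately, item 7 as printed does not measure task 7 of section 13, because a question about difficulty is scored on a discomfort scale.

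**What to change.** Keep the 6-of-7 and 85%-of-participants rules. In section 13 and the Phase II sheet in section 16:

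1. State which items make up Outcome 2. Report it as the number out of 16 with all of them correct: items 1 to 5, or items 2 to 5 if the sponsor confirms that item 1 is knowledge only. Report the 6-of-7 result separately and label it a composite pass rate.
2. Specify that the Phase II percentage of correct answers is reported by item as n/16, and that any task with concentrated failures is addressed in the study conclusion.
3. Report items 6 and 7 separately, and reword the item 7 options as levels of difficulty.

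**Cost.** Some wording, one descriptive table and one relabelled item. All other scores are already on the form. With items 1 to 5, the correct-use percentage can exceed the composite pass rate only if some subjects with all five correct give both worst self-ratings; otherwise it will be equal or lower. With items 2 to 5, it could also be higher if subjects with all four tasks correct miss item 1 and give one worst self-rating (5/7). The sponsor should expect a figure that is usually less favourable than the pass rate.
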